### **Regulatory and Ethical Considerations**

The study may be prematurely terminated due to the following events:

- Serious adverse event determined to be related to the NOWDx COVID-19 Test
- Interim analyses of study data show poor correlation of the NOWDx COVID-19 Test
- Any other unforeseen reasons

NOWDx will ultimately determine if the study or portions of the study need to be terminated prematurely. Study records will be made available for monitoring, auditing, IRB review, and regulatory inspection.

The protocol, informed consent document, and other relevant study documents will be submitted for IRB review and must be approved before the study is initiated. In addition, any subject recruitment materials must be approved by the IRB prior to being used.

Any changes to the protocol, informed consent form, or other relevant study documents will be submitted for IRB review and approval before implementation. A protocol change intended to eliminate an apparent immediate hazard to subjects may be implemented immediately provided the reviewing IRB is notified per their relevant policies.

This study will be conducted in accordance with all applicable government regulations and local institutional research policies and procedures.

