## **Study Objectives**

The purpose of this study is to generate NOWDx COVID-19 Test performance data to support FDA POC EUA of the device with capillary blood from a finger stick, and POC EUA of the device with venous whole blood from a blood draw.

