## **Study Duration, Planned Enrollment, and Number of Sites**

Studies will be performed for the period July 20, 2020 through Aug 31, 2020. Total planned enrollment is 60 study participants. Studies will be performed at CLIA waived study sites. Participants will be varied in age, gender diverse, ethnically and racially diverse, economically diverse, and with different levels of education.

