## Statistical Considerations

The study is designed to support POC EUA of the ADEXUSDx® COVID-19 Test. Clinical study data will be analyzed to assess the performance of the NOWDx COVID-19 Test. Specifically, specificity and sensitivity of the NOWDx COVID-19 Test will be determined relative to an emergency use authorized molecular (PCR) assay. The data must demonstrate a minimum overall 90% positive percent agreement (PPA) and overall 95% negative percent agreement (NPA) with point estimates not lower than 90% for combined PPA and not lower than 93% for combined NPA.

All data will be subject to performance of routine interim analyses. Results from interim analyses will help determine if the clinical trial needs to be halted due to study performance problems.

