## Study Administration

### **Data Collection and Management**

A data management plan (DMP) will serve as an outline for how data are to be handled during the study and after the study is completed.

Each study site PI will carefully monitor study procedures to protect the safety of study participants, the quality of the data, and the integrity of the study. All participant study materials will be assigned a unique identifying code called a Participant ID. The key to the code will be kept in a password protected file for the duration of the study. Only IRB approved study personnel at the Sponsor and the study site will have access to the code and information that identifies site specific study participants.

Paper or electronic study documents may be used in this study. Site operators will be given detailed operator instructions. All paper study documents must be scanned and emailed daily to [[contact]](mailto:[contact]). If internet connectivity is impaired, paper forms may be faxed to [contact] initially, then scanned and emailed upon reactivation of internet connection.

All paper study documents received from the sites will be stored on Microsoft SharePoint. Data will be entered into the database and are subject to independent data entry review at the time of data entry and during database audits. All EUA molecular (PCR) test reports received will be stored on Microsoft SharePoint. These data are also subject to independent data entry review at the time of data entry and during database audits.

Database audits will be performed bi-weekly and prior to performance of biweekly interim analyses to ensure reconciliation of relevant data (e.g. survey data, other relevant study forms).

The FDA and local regulatory authorities may inspect all study documents. If any results of the study are published, participant data will be de-identified.

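### Does the sponsor's power to end portions of the study for poor correlation at interim inflate the combined PPA and NPA?

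*Protocol*

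**What the plan says.** Three parts of the protocol bear on this point.

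- **Statistical Considerations** measures performance by sensitivity and specificity against an authorized PCR assay. It asks for 90% PPA and 95% NPA overall, with "point estimates not lower than 90% for combined PPA and not lower than 93% for combined NPA". On interim looks it says: "Results from interim analyses will help determine if the clinical trial needs to be halted due to study performance problems". The object there is the trial, not a part of it.
- **Data Collection and Management** sets the timing: "Database audits will be performed bi-weekly and prior to performance of biweekly interim analyses".
- **Regulatory and Ethical Considerations** lists three grounds on which the study may end early: a related serious adverse event, "Interim analyses of study data show poor correlation of the NOWDx COVID-19 Test", and "Any other unforeseen reasons". A separate sentence then says who decides: "NOWDx will ultimately determine if the study or portions of the study need to be terminated prematurely".

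The word *portions* occurs only in that last sentence and is not defined. It could mean a site ("Studies will be performed at CLIA waived study sites"; the number is not given) or one of the two specimen methods, since Study Objectives seeks authorization for the "device with capillary blood from a finger stick, and POC EUA of the device with venous whole blood". The protocol does not say what happens to results already obtained from an ended portion.

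**The concern.** Two things look wrong. First, the interim ground is phrased as correlation, while the test is accepted or rejected on PPA and NPA. If they were different measures, the study could be stopped on something it is not judged by.

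Second, and more serious, the sponsor sees results every two weeks, may end part of the study, and is then judged on a combined estimate. Ending the worse-looking part reduces its weight in that estimate, or removes it altogether if its data are set aside. The reported PPA or NPA would then be too high and a pass too likely, in a study meant to support an emergency use authorization. The power to end portions stands in the protocol itself, so an unseen analysis plan would not obviously cancel it.

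**Working it through.** **1. What the text attaches to what.** The list containing the correlation ground opens by speaking of the study being terminated, and Statistical Considerations speaks of halting the trial. The sentence with *portions* is about who decides. It covers safety and unforeseen reasons as well as performance. Ending one part for its interim performance is therefore a permitted reading, not a stated rule. As for the measure, no correlation coefficient appears anywhere. Statistical Considerations ties interim halting to performance and specifies performance as sensitivity and specificity against PCR. Correlation is most naturally loose wording for agreement.

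**2. Baseline.** The protocol gives no power or operating characteristic to reproduce. Each cohort has 30 participants, so the marks are 27/30 = 90.0% for PPA, and for NPA 28/30 = 93.3% (93% mark) or 29/30 = 96.7% (95% mark). Binomial chances without any stopping:

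- P(X ≥ 27 | 30, 0.85) = 0.322
- P(X ≥ 28 | 30, 0.90) = 0.411
- P(X ≥ 29 | 30, 0.90) = 0.184

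**3. Halting the whole study.** If a halted study counts as no pass, P(pass and not halted) ≤ P(pass), whatever the trigger. Assume true PPA 95% and NPA 97%, one method and the 93% NPA mark. The pass chance is 0.883 with no halting. It is 0.863, 0.796 or 0.608 with interim PPA/NPA floors of 80/90%, 90/90% or 90/93%. The loss is 2 to 27 points, depending on an assumed floor, and it falls on the sponsor.

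**4. Ending one of two portions.** Assumptions: two independent portions of 30 positives; looks after 10 and 20 (20 July to 31 August is 42 days, so two-weekly looks with even accrual fall at thirds); the weak portion is ended if its PPA is below a floor; a pass is a combined PPA ≥ 90%. Exact enumeration gives these pass chances:

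| True PPA | Floor | Both complete | Ended, data kept | Ended, data dropped |
|---|---|---|---|---|
| 95% / 80% | 90% | 0.359 | 0.638 | 0.914 |
| 95% / 80% | 80% | 0.359 | 0.454 | 0.733 |
| 95% / 80% | 70% | 0.359 | 0.371 | 0.500 |
| 95% / 85% | 90% | 0.607 | 0.745 | 0.919 |
| 87.5% / 87.5% | 90% | 0.364 | 0.368 | not used here |

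In the first row, mean combined PPA is 87.5% complete, 89.8% kept and 94.4% dropped. In the last row it is 87.5% complete and 87.1% kept. Upward bias thus needs either dropped data or portions that truly differ. When data are kept, its size depends on the assumed gap and floor.

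**5. Fit to this trial.** Thirty positives are planned in total, so two portions of 30 cannot be sites. They could be the two methods, but those use the same participants and are not independent. Allowing maximal dependence gives 0.39, 0.63 and 0.92 in place of the first row, so independence is not what drives the size.

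For sites, take 30 positives split equally over 2, 3 or 5 assumed sites, with the worst site ended at a halfway look if below the criterion (400,000 simulations):

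- Equal sites, PPA 0.85, data kept, places refilled: mean 0.850, pass 0.32. No change.
- Equal sites, data kept, places not refilled: mean PPA falls to 0.847–0.849. The pass chance is 0.21–0.33 against 0.32.
- For NPA at true 0.90, not refilled, the mean falls to 0.896–0.899. The chance of reaching 93% falls from 0.41 to 0.26–0.33, while that of reaching 95% rises from 0.18 to 0.21–0.27. The rise is a rounding effect: with two sites, one error is allowed in 22 results (21/22 = 95.5%) as well as in 30.
- Unequal sites (0.75, 0.90, 0.90), data kept: mean PPA 0.850 becomes 0.860 (not refilled) or 0.865 (refilled). Pass 0.32 becomes 0.30 or 0.41.
- Equal sites, data dropped: mean PPA 0.870–0.884, pass 0.44–0.58.

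The consistently large effects again come from dropping data.

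**The case for a change.** The best case for a change is that this is not a missing stopping boundary. The protocol itself names a measure other than PPA/NPA, gives the sponsor alone the decision, and allows parts to be ended. An analysis plan could add a threshold and leave all three in place. Keeping the data does not fully protect the estimate when the parts truly differ (0.359 to 0.638 in the first row of the table), and a few sentences with no added participants would close the gap.

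Part of this stands. The wording is loose, *portions* is undefined, and if a part were ended for its results and then left out, the combined estimate would be biased upward. But that outcome needs several steps the protocol does not take: a part ended for performance rather than the study, and then its valid results excluded or a real gap between parts. Which results enter the reported PPA and NPA is ordinary analysis-set content, and a competent analyst would keep every valid result.

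The one remedy that goes further is to forbid any performance halt until the criterion can no longer be met, that is, at the 4th false negative of 30. That would also bar the sponsor from closing a site with evident operator problems. It trades useful discretion for protection against a scenario the text only permits, and a sponsor could reasonably decline it. On the method reading, ending one method would also cost the sponsor data for an authorization that Study Objectives seeks.

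**Conclusion.** The concern does not call for a change. Correlation for agreement is a slip of wording. The undefined *portions* and the unstated retention of data are details that an analysis plan or the analysts would fill in the obvious way, by keeping all valid results. Under that handling, equally performing parts give no material inflation (36.4% against 36.8%, mean PPA 87.5% against 87.1%), apart from rounding shifts in small samples. Truly unequal sites, as assumed above, move mean PPA by 1.0 to 1.5 points. The striking figures, up to a 91% pass chance, require dropped data. The 64% figure requires a 15-point gap between portions of 30 positives and a 90% interim floor; at a 70% floor it is 37%. Number of sites, look timing, floors, true rates and dependence between methods are all assumptions. The conclusion would change if a document showed that an ended portion's results are to be excluded from the combined PPA or NPA.

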### **Risks and Benefits**

The possible risks associated with participating in this study are described in this section. The risks to a healthy person of donating small blood samples from a finger stick or venipuncture are very small. Possible risks include

Title: NOWDx COVID-19 EUA Blood Test CLIA Waiver Trial

Sponsor: NOWDiagnostics, Inc.

bruising, pain, soreness, bleeding, infection, or inflammation of the puncture sites, and light-headedness or fainting. The discomfort of the procedure is the same or less as a routine blood draw. In addition to the risks listed above, participants may experience a previously unknown risk or side effect. This research project is not expected to present additional risk to the fetus for pregnant women as samples collected from pregnant women will be like those collected over the normal course of pregnancy. Risk for infection is minimized in the study design by providing instructions to use an alcohol swab on the area of specimen collection prior to finger stick to disinfect the puncture surface. The same risk is minimized by disinfection using alcohol swabs at the site of puncture prior to venipuncture, which is common practice in standard of care. Risk for pain during capillary blood collection is minimized through utilization of the Unistik Comfort Zone Technology®, technology inherent in lancets to be employed for all finger stick study procedures and designed to reduce pain for more comfortable sampling.

| Possible Risk/Side Effect | How often has it occurred? | How serious is it?    | Can it be corrected?  |
|---------------------------|----------------------------|-----------------------|---|
| Infection                 | Extremely uncommon         | Very serious          | Report to a healthcare professional immediately for assessment and possible antibiotic treatment          |
| Light-headedness          | Common                     | Can be easily treated | If you feel dizzy, tell a healthcare professional. The feeling will pass after you rest and drink fluids. |
| Bruise on finger          | About half of people       | Can be easily treated | No long-term effects  |
| Pain                      | Common                     | Mild                  | No treatment needed   |
| Soreness                  | Uncommon                   | Mild                  | No treatment needed   |
| Excessive Bleeding        | Extremely uncommon         | Can be easily treated | No long-term effects  |
| Inflammation of site      | Extremely uncommon         | Can be easily treated | Usually goes away without treatment   |

There will be no direct benefits to the study participants; however, knowledge gained from the study could potentially benefit participants in the future.

#### **Informed Consent and HIPAA Authorization**

The Informed Consent will include HIPAA Authorization. Specifically, participants will provide explicit authorization to use or disclose their protected health information (PHI) required for study performance and prior to study enrollment.

The Informed Consent specifies PHI to be provided by participants during study conduct, specific information about who may use or disclose the PHI as a direct result of the participant providing authorization, and details of each use or disclosure that will be a result of the authorization. An individual providing authorization must understand any way that their information is planning to be used or disclosed. The Informed Consent also specifies the date of expiration where the authorization is no longer valid, and PHI can no longer be used or disclosed. Finally, all prospective participants must provide their authorization via signature on the Informed Consent.

#### **Safety Monitoring**

The study site PI or designated site operator at the study site will be responsible for monitoring the participant for any adverse event (AE) and/or serious adverse event (SAE). All AEs and SAEs will be recorded on the relevant participant case report form as well as an Adverse Event/Serious Adverse Event Report Form. All SAEs will be reported to NOWDx using the designated form within 24 hours of the site learning of the event. The study

Title: NOWDx COVID-19 EUA Blood Test CLIA Waiver Trial  
Sponsor: NOWDiagnostics, Inc.

site PI will be responsible for follow-up of any SAE until a final outcome is established and the outcome is recorded in the Adverse Event/Serious Adverse Event Report Form.

AEs will include any unfavorable and unintended sign, symptom, or disease temporarily associated with the use of a NOWDx COVID-19 Test.

SAEs will include any event that results in death, is life-threatening, requires hospitalization (admission for longer than 24 hours or prolongation of a current hospital stay), results in disability or permanent damage (substantial disruption of a person's ability to conduct normal life functions), or requires intervention to prevent permanent impairment or damage.

### **Retaining Samples**

Following clinical study performance by site operator 2 of the ADEXUSDx® COVID-19 Test according to the Transfer Device Method (Waived) Instructions for Use, plasma sourced from EDTA/lavender-top tubes will be frozen and shipped to NOWDx.

Plasma may be used to perform necessary analytical or clinical tests to support FDA EUA or clearance of the NOWDx COVID-19 Test including, but not limited to, repeat testing in the event of invalid or discrepant test results or additional testing requested by the FDA following EUA or 510(k) CLIA Waiver submissions.

With participant consent, remaining plasma samples may be stored deidentified indefinitely following clearance of the NOWDx COVID-19 Test for future testing to support additional NOWDx COVID-19 Test indications for use, such as expanded use of the NOWDx COVID-19 Test with an analyzer. Remaining samples will not be shared with secondary researchers.

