## **Abstract**

This study is designed to test the performance and demonstrate effectiveness of the NOWDiagnostics, Inc. (NOWDx) COVID-19 Test for the detection of antibodies in response to SARS-CoV-2 infection. ADEXUSDx® is the registered brand of the COVID-19 antibody test intended for point of care (POC), also known as CLIA waived, use.

The study will be performed by CLIA waived site operators, representative of intended users of the ADEXUSDx® COVID-19 Test, to support U.S. Food and Drug Administration (FDA) Emergency Use Authorization (EUA) of the device. Site operators will perform tests on enrolled participants via finger stick method with capillary blood.

Venous whole blood samples will also be collected from participants per local standard phlebotomy procedures at the study sites and will be used by site operators to perform tests via transfer device method.

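### Does the allowance for repeat testing of invalid or discrepant results on frozen plasma bias PPA and NPA upward?

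*Protocol*

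**What the plan says.** Study Objectives limits the performance claim to two specimen types: "capillary blood from a finger stick, and POC EUA of the device with venous whole blood from a blood draw". The Abstract says who produces the data: "The study will be performed by CLIA waived site operators, representative of intended users of the ADEXUSDx® COVID-19 Test". Under Study Procedures, site operator 1 runs the finger-stick test and site operator 2, blinded to that result, runs the transfer-device test on venous blood. Each completes a case report form.

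Statistical Considerations bases performance on the clinical study data. Sensitivity and specificity "will be determined relative to an emergency use authorized molecular (PCR) assay". The pass marks are 90% overall PPA and 95% overall NPA, with "point estimates not lower than 90% for combined PPA and not lower than 93% for combined NPA".

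Retaining Samples, under Study Administration, covers what happens to the plasma after site operator 2 has finished. It is frozen and shipped to the sponsor, and it may be used for analytical or clinical tests that support the EUA or clearance. The list of uses is expressly not exhaustive. Its named examples are "repeat testing in the event of invalid or discrepant test results or additional testing requested by the FDA". Study Procedures adds that all remaining samples go to the sponsor at study end for whatever further testing is needed.

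**The concern.** Discrepant analysis is a known source of bias in diagnostic accuracy studies. If only the results that disagree with the comparator are repeated, and the repeat replaces the first result, a disagreement can become an agreement but never the reverse.

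Several features of this protocol raise that suspicion:

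- The named trigger for a repeat is the result itself, and the stated purpose is regulatory support.
- The repeat would use frozen plasma at the sponsor. The claim is for fresh capillary or venous whole blood tested by waived-site operators.
- The sponsor receives study forms daily, holds the PCR reports and runs biweekly interim analyses. It could therefore know which results disagree before it chooses what to retest.
- No sentence says that the first site result stands.

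Cohorts are small ("Total planned enrollment is 60 study participants", 30 in each), so one or two reversals could decide whether a pass mark is met.

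**Working it through.** **Inputs.** From the protocol: n = 30 per cohort; PPA mark 90%; NPA marks 95% (overall) and 93% (combined). Assumed, because the protocol gives no values: the true agreement p, and the probability r that a retest of a PCR-discordant result comes out concordant. The protocol states no power or error rate, so there is no figure of its own to reproduce.

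**Pass marks as counts.** 0.90 × 30 = 27, so PPA needs 27/30 (90.0%). 0.93 × 30 = 27.9, so the 93% NPA mark needs 28/30 (93.3%). 0.95 × 30 = 28.5, so the 95% NPA mark needs 29/30 (96.7%).

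**If retests replaced PCR-discordant results.** Effective agreement is p + (1 − p) × r, and the chance of passing is an exact binomial tail with n = 30. For PPA with p = 0.85 and r = 0.50, effective agreement is 0.85 + 0.15 × 0.50 = 0.925.

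| Assumed r | PPA, p = 0.85: P(≥27/30) | NPA, p = 0.90: P(≥28/30) | NPA, p = 0.90: P(≥29/30) |
|---|---|---|---|
| 0 | 0.322 | 0.411 | 0.184 |
| 0.10 | 0.409 | 0.486 | 0.234 |
| 0.25 | 0.559 | 0.607 | 0.331 |
| 0.50 | 0.816 | 0.812 | 0.554 |

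Under substitution the effect would be large against either NPA mark.

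**Is the direction always upward?** Only for results discordant with PCR. The clause also covers invalid results, and it does not say whether a discrepancy is against PCR or between the two operators.

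- *Invalid results.* Suppose 26 of 28 valid results agree (92.9%) and 2 are invalid. After retesting the two, agreement is 26/30 (86.7%), 27/30 (90.0%) or 28/30 (93.3%). It can move either way.
- *Operator against operator.* Suppose that in the positive cohort finger stick gives 28/30 and transfer device 25/30, with three people differing between methods. Combined agreement is 53/60 (88.3%). If one retest replaces both results for those three, it becomes anything from 50/60 (83.3%) to 56/60 (93.3%). It can fall.

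**Does the protocol make the substitution?** Statistical Considerations takes agreement from clinical study data. Study Procedures, the Abstract and Study Objectives identify those data as site-operator results on capillary and venous whole blood. Retaining Samples starts after those tests are complete and sits under Study Administration. It neither requires a retest nor restricts retesting to disagreeing samples, and it assigns no retest a role in PPA or NPA. There is one plasma tube per participant but two site results, and no rule maps one to the other, as a substitution rule would need. Read together, the sections give r = 0, the first row of the table.

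**The case for a change.** The strongest counter-argument is that this is more than silence. The protocol affirmatively authorises repeat tests triggered by results, in support of the EUA, on a specimen outside the claim. The sponsor can see which results disagree, and the calculation shows how much substitution could matter at n = 30. A sentence fixing the first site result would cost almost nothing.

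Much of this stands as fact. The clause exists, plasma is not a claimed specimen, the meaning of discrepant is left open, and no sentence expressly says that first results stand. The arithmetic is also right on its assumptions.

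What does not stand is the step from permission to retest to a biased estimate. Repeat tests can support an EUA as root-cause investigation, as analytical work or as answers to regulator queries without altering PPA or NPA. Nor does the text say that only disagreeing samples are retested, since the list of uses is open.

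One reply to the size of the effect carries limited weight. If combined agreement pools the two methods, the denominator is 60 and one reversed result moves it by 1/60 (1.7 points) instead of 1/30 (3.3 points). But a single plasma retest that overrode both of a participant's results would move it by 2/60, again 3.3 points.

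**Conclusion.** No change to the protocol follows. An analyst who follows it computes PPA and NPA from the results that site operators recorded, and those estimates are not affected by plasma retesting. The rise in the chance of passing from 0.32 to 0.82 depends on three assumptions that the protocol does not supply: that retests replace site results, that only PCR-discordant samples are chosen, and that half of them reverse (with true PPA at 85%).

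What remains is unwritten detail: which result counts after a repeat, how invalid results enter the denominator, and what discrepant refers to. Such rules commonly belong in the SAP, which may exist but is not shown, so their absence from the protocol is not a fault. The natural default, that the first site result per method is analysed and plasma retests are reported separately, fits the stated objectives. This conclusion would change if the SAP let plasma retests replace site results.
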